### **9.3.1 Primary Analyses**

#### **9.3.1.1 Hot Flash Frequency, Week 6 (Day 42)**

Mixed models repeated measures (MMRM) analyses that incorporate, treatment, time, and the treatment\*time interactions will be the primary analytical method for the percentage change in the frequency of moderate to severe hot flashes. The percentage change from baseline in frequency of moderate to severe hot flashes in each active arm will be compared to the placebo arm at Week 6 (Day 42). The analysis will be handled in two ways within the MMRM framework: (1) the means analysis comparing the change from baseline to Week 6, and (2) the slope analysis comparing the rate of change from baseline to Week 6.

The primary endpoint in the study will be analyzed when the last patient reaches Day 42. However, the clinical site and patients will remain blinded through the completion of the Day 84 efficacy assessments and the follow up safety visits.

Each subject's hot flash frequency will be summed on a weekly basis. Because the MMRM is the primary analytical method, it will be possible to estimate Week 6 changes from baseline by incorporating the preceding weeks' data, e.g., Week 6 estimates will incorporate data from baseline and Week 1 through Week 6. Analyses will be performed for the EE (EEIA) populations.

If the MMRM model does not converge or has poor fit, T-tests or non-parametric tests, if the data are deemed non-normally distributed, will compare changes over time within (Paired T-test or Wilcoxon sign-rank test) an arm and between (T-test or Wilcoxon rank sum test) each active arm and the placebo arm, respectively.

The Hochberg procedure (Hochberg Y, 1988) will be applied to control for the multiple comparisons associated with the comparisons between the two dose arms and placebo and the two different MMRM analyses (means, slope) in the primary analyses of frequency of hot flashes in Stage 1. The analyses for Stage 2 will be treated similarly to address the multiplicity of the MMRM analyses. Note that the placebo arm in Stage 2 comprises a cohort of subjects distinct from those placebo subjects that were enrolled during Stage 1.

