## 5. ANALYSIS POPULATIONS

The subjects will be over the age of 18 and will have moderate to severe hot flashes, defined as a minimum of 4 moderate to severe hot flashes per day or 12 per week at baseline. The 4populations are as follows:

Intent-to-Treat (ITT) population:	All enrolled subjects who have taken at least 1 dose of study drug.
Efficacy Evaluable (EE) population:	All subjects in the ITT population who have analyzable baseline data and 12 weeks of hot flash data. Subjects must also be at least 80% compliant with taking study drug with no major protocol deviations, including no major inclusion/exclusion deviations.

Efficacy Evaluable (EEIA) population for IA:	All subjects in the ITT population who have analyzable baseline data and 6 weeks of hot flash data. Subjects must also be at least 80% compliant with taking study drug with no major protocol deviations, including no major inclusion/exclusion deviations.
Safety population:	All subjects who receive at least 1 dose of study drug. The safety analyses will be conducted on this population. This population is the same as the ITT population.

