## Data Handling

Baseline week will be determined from the second week of the first two weeks of hot flash eDiary that were recorded; if a patient qualified for study entry by number of hot flashes during the second week of screening, then data from that week will be used as their baseline. However, if a patient did not qualify for study entry based on the number of hot flashes during that second week then data from the screening week that was used to qualify the patient will be used as their baseline instead. A week's data collection will be considered the 6 days prior to plus the day of week's data. For example, Week 6 data will include the data collected for the 7 days from Day 36 through Day 42, inclusive. For a subject's data to be considered non-missing for a given week the subject must have recorded at least 4 days of data during the respective week. For subjects who report at least 4 days of data during a week, the weekly frequency of moderate and severe hot flashes will be the sum across those days of the number of moderate to severe hot flashes. The severity level reported for each of the reported hot flashes will be calculated as follows. Baseline severity level will be the number of severe hot flashes reported times 3 + the number of moderate hot flashes reported times 2 then divided by the number of moderate and severe hot flashes reported. Post-baseline weeks will have their severity level calculated as above but with the addition of reported mild hot flashes so the post-baseline severity for a given week level will be the number of severe hot flashes reported times 3 + the number of moderate hot flashes reported times 2 + the number of mild hot flashes reported times 1 then divided by the number of mild, moderate and severe hot flashes reported. The percentage change from baseline of the frequency of moderate and severe hot flashes will be the number of moderate to severe hot flashes reported for the given week minus the number reported at baseline then divided by the number reported at baseline and converted to a percentage by multiplying by 100. The percentage change from baseline of the severity of moderate and severe hot flashes will be the calculated severity score reported for the given week minus the severity score at baseline then divided by the severity level reported at baseline and converted to a percentage by multiplying by 100.

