## 6.3.1.1 Primary Efficacy Endpoint Analysis (Hot Flash Frequency at Week 6)

STAGE 1:

The primary frequency efficacy endpoint is percentage change in frequency of moderate and severe hot flashes (vasomotor symptoms) from the baseline week to Week 6 (Day 42). The statistical tests for significant differences with regards to the percentage change between placebo and each of the active arms, 10 mg 50mg, and perhaps 100 mg comprise the main tests of interest.

The SAS code for performing the MMRM analyses to test for a significant difference in the MEAN percentage change in frequency of moderate to severe hot flashes between each of the dose arms and placebo evaluated at Week 6 (primary analysis week) is shown below. Note that this analysis will generate two of the four tests that are part of the primary analysis to which the Hochberg procedure will apply.

PROC MIXED DATA= XXX; CLASS subjid tx week; MODEL cfb = tx week\_2 tx\*week\_2; REPEATED week / type=AR(1) sub=subjid(tx); LSESTIMATE tx\*week '10MG VS Placebo at Week 6' [1, 10 6] [-1, P 6]; LSESTIMATE tx\*week '50MG VS Placebo at Week 6' [1, 50 6] [-1, P 6]; WHERE week le 6; RUN;

The variables used in the above model will be defined as follows: tx=treatment; week (1, 2... 6); cbf=change from baseline value, week\_2=week (week will be treated as a categorical variable in the class statement and week\_2 will be treated as a continuous variable in the model... effectively the values of these variables will be an exact match). By creating week\_2 in a preceding data step, this allows for LESTIMATES to be computed at a specific WEEK (treated as categorical in the CLASS statement) but allows week to be treated as a continuous variable, WEEK\_2 in the model.

This model will be run 3 separate times using 3 separate covariance structures to determine best fit. The same model will be run, with the following specified change on the REPEATED line: (1) type=AR(1); (2) type=CS; and (3) type=UN. If a model does not converge, then disregard that model. If more than 1 model remains, then refer to the Akaike's Information Criteria (AIC) score to determine model fit. The best fit model will be chosen as having the AIC value closest to zero. The model type chosen will be referenced in the footnote for each model output.

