Additional prespecified analysis of the data will be conducted regardless of whether the MMRM model(s) converge, and will be considered the definitive tests for significance in the event the MMRM model(s) do not converge:

• T-tests will be generated to compare the percentage change from baseline to each of Week 6 in the placebo arm to each of the 10 mg and 50 mg arms. If the data are determined to be non-normally distributed then the Wilcoxon rank sum test will be the definitive test of significance.

• Wilcoxon rank sum tests will be generated to compare the percentage change from baseline to Week 6 in the placebo arm to each of the 10 mg and 50 mg arms.

The SAS code for performing the MMRM analyses to test for a significant difference in the SLOPES of the percentage change in frequency of moderate to severe hot flashes between each of the dose arms and placebo by Week 6 (primary analysis week) is shown below. Note that these analyses will generate the remaining two of the four tests that are part of the primary analysis to which the Hochberg procedure will apply.

The where statement in PROC MIXED has been used to simplify the interpretation of the output so that one model will be run for the 10 mg versus placebo slope analysis and a separate one for the 50 mg versus placebo slope analysis through Week 6. Variable have the same meaning as defined in the above analysis.

PROC MIXED DATA=XXX; CLASS subjid tx; MODEL cfb= tx week tx\*week / s; RANDOM intercept week/ type=AR(1) sub=subjid g; WHERE tx in (10, P) and week le 6; /\* repeat for 'tx in (50, P)' \*/ RUN;

This model allows for both the intercept and the slope to differ randomly for each subject but the overall p-value for the interaction term is interpreted as a test of the slope between the stated active arm and placebo. Note, if the p-value is significant, the estimated coefficients must be in the appropriate direction to conclude the result is in favor of the active dose arm.

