## 6.3.2 Secondary Efficacy Variables

As noted previously, the same MMRM models - one for means and one for slopes - specified for the primary analysis will be used for each of the following hot flash related secondary endpoints including both frequency of hot flashes and severity of hot flashes.

#### 6.3.2.1 Percentage Change in severity of moderate and severe hot flashes from baseline to week 6

Analyzed with the same methods and considerations as for the analysis of frequency at week 6 (primary endpoint). Please see the data handling description (Section 6.3.1) for the specifics of severity calculation Repeat for Stage 2 as necessary.

## 6.3.2.2 Percentage Change in frequency of moderate and severe hot flashes from baseline to week 8

Analyzed with the same methods and considerations as for the analysis of frequency at week 6 (primary endpoint). Repeat for Stage 2 as necessary.

## 6.3.2.3 Percentage Change in frequency of moderate and severe hot flashes from baseline to week 10

Analyzed with the same methods and considerations as for the analysis of frequency at week 6 (primary endpoint). Repeat for Stage 2 as necessary.

#### 6.3.2.4 Percentage Change in frequency of moderate and severe hot flashes from baseline to week 12

Analyzed with the same methods and considerations as for the analysis of frequency at week 6 (primary endpoint). Repeat for Stage 2 as necessary.

#### 6.3.2.5 Percentage Change in severity of moderate and severe hot flashes from baseline to week 8

Analyzed with the same methods and considerations as for the analysis of frequency at week 6 (primary endpoint). Please see the data handling description (Section 6.3.1) for the specifics of severity calculation Repeat for Stage 2 as necessary.

## 6.3.2.6 Percentage Change in severity of moderate and severe hot flashes from baseline to week 10

Analyzed with the same methods and considerations as for the analysis of frequency at week 6 (primary endpoint). Please see the data handling description (Section 6.3.1) for the specifics of severity calculation Repeat for Stage 2 as necessary.

#### 6.3.2.7 Percentage Change in severity of moderate and severe hot flashes from baseline to week 12

Analyzed with the same methods and considerations as for the analysis of frequency at week 6 (primary endpoint). Please see the data handling description (Section 6.3.1) for the specifics of severity calculation Repeat for Stage 2 as necessary.

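### The means MMRM does not adjust the Week 6 contrast for baseline hot flash frequency, although every analysed man has a baseline value; adding it is a cheap, modest improvement

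*SAP*

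**What the plan says.** SAP 6.3.1.1 gives code for the means model, whose stated purpose is "to test for a significant difference in the MEAN percentage change in frequency of moderate to severe hot flashes". Its model statement holds treatment, week and their interaction only, "MODEL cfb = tx week\_2 tx\*week\_2", with a repeated-measures covariance over weeks. Protocol 9.3.1.1 describes the same content in words, in the sentence that opens "Mixed models repeated measures (MMRM) analyses that incorporate, treatment, time, and the". Neither lists a baseline covariate. The companion slope model, "MODEL cfb= tx week tx\*week / s" with a random intercept and slope, has none either. The fallback t-tests and Wilcoxon tests are also unadjusted.

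Baseline enters only through the outcome. Under Data Handling in SAP 6.3.1, percentage change is the week's count "minus the number reported at baseline then divided by the number reported at baseline and converted to a percentage". The baseline count comes from one diary week: the second screening week or, if that week did not qualify the man, the week that did.

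A baseline is available for every analysed man. The Week 6 efficacy population in SAP 5 is defined as "All subjects in the ITT population who have analyzable baseline data and 6 weeks of hot flash data", with compliance and deviation conditions added, and the outcome cannot be computed without a baseline.

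Protocol 7.1 describes 1:1:1 randomisation in Stage 1 and 1:1 in Stage 2 and names no stratification factor. SAP 6.3.2 carries the choice of model forward, stating: "one for means and one for slopes - specified for the primary analysis will be used for each of the following hot flash related secondary endpoints". SAP 6.3.1.1 reuses them for Stage 2.

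**The concern.** Dividing by baseline does not make the result independent of baseline. A man whose baseline week was high by chance will tend to show a larger percentage fall whatever he receives. A minimum count for entry, and a rule that can make the qualifying week the baseline, both strengthen this regression to the mean. Some of the spread in the outcome is then predictable from a number already held, and the means model leaves it in the error term.

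Two things are at stake, both modest. The Week 6 contrast may be less precise than it could be. And if two small arms differ at baseline by chance, part of that difference passes into the estimate. The Week 6 result matters because it informs whether Stage 2 opens (SAP 6.7). The arms can also shrink below 30, since dropouts are not replaced (Protocol 8.12) and the efficacy populations exclude men.

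**Working it through.** **1. The plan's own figure.** SAP 6.1.4 gives 30 per arm for one-sided alpha 0.10, 90% power, a 40% lower frequency than placebo, and variance equal to the active-arm mean. With placebo mean m, the difference is 0.4m and the variance 0.6m, so

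n = 2 × (1.2816 + 1.2816)² × 0.6m / (0.4m)² = 49.3/m.

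The placebo mean is not given, so 30 cannot be confirmed. It requires m = 49.3/30 = 1.64. At the entry minimum of 12 per week, n = 49.3/12, or 5. Read as a daily rate (12/7 = 1.71), n = 29. No baseline correlation enters this calculation, so the point here does not depend on it. I use only the standardised effect that 30 per arm detects with 90% power: √(2 × 2.5631²/30) = 0.662 SD.

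**2. Correlation of percentage change with baseline (assumed inputs).** The documents give no typical weekly count, week-to-week variation or spread of response. Counts were simulated with the 12-per-week entry rule. Three of the 18 settings:

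| Typical weekly count | Week-to-week overdispersion | Between-man spread of response | Correlation with log baseline |
|---|---|---|---|
| 20 | 0.02 | 0.6 | -0.08 |
| 35 | 0.10 | 0.3 | -0.28 |
| 50 | 0.25 | 0.3 | -0.38 |

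The first and last are the extremes of the 18. A separate simulation, with medians of 14-45 and week-to-week CVs of 15-35%, gave -0.07 to -0.36. A fair working range is -0.1 to -0.35.

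**3. Effect on the Week 6 means contrast.** Adjustment multiplies the variance by (1 - ρ²). Estimating the coefficient with two arms of 30 costs a factor of 1 + 1/(60 - 4) = 1.018. Net power is Φ(0.662 × √15 / √f - 1.2816), where f is the net factor.

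| Size of ρ | 1 - ρ² | Net factor f | Net power |
|---|---|---|---|
| 0 | 1.000 | 1.018 | 89.6% |
| 0.1 | 0.990 | 1.008 | 89.8% |
| 0.2 | 0.960 | 0.977 | 90.5% |
| 0.3 | 0.910 | 0.926 | 91.7% |
| 0.35 | 0.878 | 0.893 | 92.4% |

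Unadjusted power is 90.0%. Break-even is at 1 - ρ² = 1/1.018, so ρ is about 0.13. The separate simulation in step 2 gave net variance changes from about a 1% loss to a 13% gain; at f = 0.87 the power is 92.9%.

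**4. Chance imbalance.** The standardised baseline difference between two arms of 30 has SD √(2/30) = 0.258. It exceeds 0.25 SD with probability 33% and 0.5 SD with probability 5%. Unadjusted, a 0.5 SD imbalance shifts the contrast by ρ × 0.5, which is 0.15 SD at a correlation of 0.3. That is 0.15/0.662 = 23% of the effect in step 1.

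**5. The slope model.** With complete data, a baseline main effect does essentially nothing for the treatment-by-week test; only a baseline-by-week term can. Simulated variance ratios (adjusted over unadjusted, 30 per arm) with that term:

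| Correlation of baseline with intercept | With slope | Slope contrast | Week 6 contrast |
|---|---|---|---|
| 0 | 0 | 1.03 | 1.02 |
| 0.3 | 0 | 1.02 | 0.98 |
| 0.5 | 0 | 1.02 | 0.86 |
| 0.3 | 0.3 | 0.97 | 0.86 |

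Regression to the mean shifts all post-baseline weeks alike. It therefore moves the intercept and not the slope.

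**The case against.** The strongest reply is that nothing in the plan is wrong. Randomisation protects the comparison on average, type I error is not inflated, the SAP agrees with the protocol, and the outcome already uses baseline. This is a phase 2 dose-finding trial tested at one-sided 0.10, and the gain could be nil. All of that stands. It sets the weight of the point but gives no reason to leave out a covariate that is in hand.

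Three stronger readings are tempting, and the documents do not support them.

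- *Adjustment is free and worth several men per arm.* That takes ρ² as the whole gain. The coefficient costs about 1.8% of variance, so below a correlation of about 0.13 the net effect is nil or slightly negative. The inputs that fix the correlation appear nowhere in the documents.
- *Both primary models lose precision.* The slope tests gain only if baseline predicts slope, and nothing in the documents shows that it does. Where it was unrelated, the added term left slope variance the same or up to about 3% higher.
- *The same gain applies to every hot flash endpoint.* The omission does carry to all of them, but the figures here are for counts. Severity is a bounded average score (2 to 3 at baseline, 1 to 3 afterwards), and these figures say nothing about the size of its gain.

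**Conclusion.** The point holds for the means model, as a cheap improvement and not an error. The Week 6 contrast is not adjusted for baseline frequency, although every analysed man has a value and no stratification factor is named. Over a correlation of about -0.1 to -0.35, adjustment changes the variance of the contrast by between roughly nil (at worst a 1-2% loss) and a gain of about 10-13%, or about 0 to 3 points of power at 30 per arm. It also removes most of the shift that a chance baseline imbalance would cause.

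The omission itself is certain from the text. The size rests on assumed weekly counts, week-to-week variation and spread of response between men; a wider spread of response lowers the gain.

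**What to change.** Before the unblinded Week 6 analysis:

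- In SAP 6.3.1.1, add log baseline weekly frequency and its interaction with week to the means model, for the primary and the secondary frequency endpoints in both stages.
- In SAP 6.3.2, add baseline severity to the means model for the severity endpoints.
- State the same in Protocol 9.3.1.1 and 9.3.2.1.
- Leave the slope model as it is.

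The cost is one or two degrees of freedom, about 1.8% of variance if baseline proves not to be predictive, and no new data. Timing matters: a covariate added after the Week 6 results are seen would look data-driven.

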## Adjustment for Multiple Comparisons

The Hochberg procedure will be applied to control for multiplicity for each of the primary and secondary hot flash related endpoints. Each endpoint will have 4 analyses associated with them to account for the two active dose arms (10 mg and 50 mg) each compared to baseline by two methods each (MMRM test for slope and MMRM test for change from baseline at the specified week). These may be referred to as sets of analyses. Hochberg is a step-up procedure based on univariate p-values. This procedure begins

with the least significant p-value and then examines the other p-values in sequential order, making alpha level adjustments along the way, until a significant p-value is observed. Once achieved, all following lower p-values in the sequence would be considered significant. For example, if one has 4 hypotheses the following will be performed:

- Step 1: Order the p-values from largest (least significant) to smallest (most significant)
- Step 2: Using the pre-specified overall alpha level,  $\alpha_0=0.10$ , one-sided, compare the largest p-value, P1, to the overall alpha level. If P1<0.10 then all (null) hypotheses are rejected; otherwise go to step 3.
- Step 3: Compare the second largest p-value, P2, to  $\alpha_1$ =0.10/2=0.05. If P2<0.05 then this and all further hypotheses are rejected; otherwise repeat for the third, P3, and fourth, P4, largest p-values compared with  $\alpha_2$ =0.10/3=0.033 and  $\alpha_3$ =0.10/4=0.025 as necessary to either reject all remaining hypotheses or conclude no significant difference exists.

For this study, during Stage 1, Hochberg's procedure will rank the p-values from highest to lowest for each statistical test within each set of analyses: 10 mg versus placebo slope difference (through Week 6), 50 mg versus placebo slope difference (through Week 6), 10 mg versus placebo mean difference at week 6, 50 mg versus placebo mean difference at Week 6. Adjustment for the single comparison of 100 mg versus placebo in Stage 2 will be necessary only for the two MMRM modes, means and slopes.

Overall, for the multiple tests of primary and secondary endpoint analyses alpha control will be achieved by a gate-keeping method such that the endpoints are ordered and the preceding endpoint must be shown to be significant in order for endpoints down the list to be eligible for significance.

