#### Common analytical methods for all hot flash related analyses

The MMRM analyses shown in the following section with SAS code written specifically to address the primary analysis of difference in percentage change of the frequency of hot flashes at Week 6 between each of the active arms and placebo are the **SAME** for all hot flash related analyses, both frequency and severity, at all weeks of interest. Simple changes to the data set to subset to the appropriate weeks of data and to the LSESTIMATE statements are all that is necessary to construct the appropriate tests. MMRM models that test for MEAN difference between active arm(s) at Week 6 and placebo and separately for a

difference in SLOPE between active arm(s) at Week 6 and placebo. There is no plan to compare the active arms to each other.

If the MMRM models does not converge or have poor fit, T-tests or non-parametric tests, if the data are deemed non-normally distributed, will compare percentage changes over time between (T-test or Wilcoxon rank sum test) each active arm and the placebo arm, respectively.

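### The primary means program requests its Week 6 contrasts on an effect that its model does not contain, and the SAP does not say which of two different repairs applies

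*SAP*

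**What the plan says.** **Means program (SAP 6.3.1.1).** CLASS lists `subjid`, `tx` and `week`. MODEL has `tx`, `week_2` and `tx*week_2`, where `week_2` is a copy of week kept out of CLASS. The contrasts, such as the one labelled "10MG VS Placebo at Week 6", are LSESTIMATE requests on `tx*week`. The SAP explains that creating `week_2` does two things: "this allows for LESTIMATES to be computed at a specific WEEK (treated as categorical in the CLASS statement", and it "allows week to be treated as a continuous variable".

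**Role in the primary analysis (SAP 6.3.1, Adjustment for Multiple Comparisons).** The Hochberg set has four tests: two slope tests and "10 mg versus placebo mean difference at week 6, 50 mg versus placebo mean difference at Week 6".

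**Reuse.** The common-methods part of SAP 6.3.1 applies the same code to all hot flash endpoints: "Simple changes to the data set to subset to the appropriate weeks of data and to the LSESTIMATE statements are all that is necessary". The Stage 2 part of 6.3.1.1 repeats the request on `tx*week` for 100 mg.

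**Fallback.** The t-test and Wilcoxon tests are always run. Section 6.3.1 brings them in "If the MMRM models does not converge or have poor fit"; section 6.3.1.1 says they "will be considered the definitive tests for significance in the event the MMRM model(s) do not converge".

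**Slope program (SAP 6.3.1.1).** Weeks 1–6, one active arm against placebo at a time, with "RANDOM intercept week/ type=AR(1) sub=subjid g". Protocol 9.3.1.1 describes the slope analysis as the rate of change from baseline to Week 6.

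**The concern.** LSESTIMATE forms contrasts among least-squares means of an effect in MODEL that is made up of CLASS variables. Here `week` appears only in CLASS and REPEATED. The program can converge normally and still have no `tx*week` parameters to contrast. A missing contrast is neither non-convergence nor poor fit, so the fallback is not triggered and the SAP gives no rule for this case.

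The analysis affected is the one on which the design turns. SAP 6.7 uses the Week 6 MMRM for an unblinded interim that a sponsor representative reviews, and Stage 2 starts if no dose is statistically significant. Gate-keeping then makes every secondary endpoint depend on the primary result. If the repair is first decided when the program fails on unblinded data, the primary test is no longer prespecified.

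**Working it through.** **(a) Means program**

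1. *Plan's own figures.* Hochberg levels 0.10/k for k = 1 to 4 are 0.10, 0.05, 0.033 and 0.025, as the SAP states.
2. *Parameters.* The coded model has 3 arms × (intercept + slope) = rank 6. With categorical week it has 3 arms × 6 weeks = rank 18. The coded model contains no `tx*week` cells.
3. *Reach.* One primary plus nine secondary hot flash endpoints make 10; × 2 doses = 20 mean contrasts in Stage 1 and 10 in Stage 2.
4. *Two repairs.* (A) Keep continuous week and estimate (tx difference) + 6 × (`tx*week_2` difference), which is estimable in the coded model. (B) Put categorical `week` and `tx*week` in MODEL and keep LSESTIMATE.
5. *They estimate different things.* Take a true Week 6 difference of −30 points and an unweighted line over Weeks 1–6, with mean week 3.5 and sum of squares 17.5.
   - Plateau from Week 3 (−10, −20, then −30 four times): mean −25, slope −65/17.5 = −3.71, fitted value at Week 6 = −25 + 2.5 × (−3.71) = −34.3.
   - Late onset (0, 0, 0, −10, −20, −30): mean −10, slope −110/17.5 = −6.29, fitted value −25.7.
   - Repair B gives −30 in both.
6. *Their precision differs.* Assume 30 per arm and SD 35. B: 35 × √(2/30) = 9.04. A, with compound symmetry and correlation 0.5: √[(2/30) × 612.5 × (1 + 1/6 + 2.5²/17.5)] = 7.89. Over AR(1) or CS with correlation 0.5 to 0.9, A runs from 7.89 to 9.02.
7. *How often verdicts differ.* Simulation: 3 × 30 subjects, Weeks 1–6, REML, 4,000 trials per setting, one-sided 0.10. SDs are intercept/slope/residual in percentage points. All are assumptions, as the documents give none.

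| True Week 6 difference | 30/4/15 | 35/5/15, 30/3/20, 20/8/15 |
|---|---|---|
| −15 to −20 | 8–11% | 9–12% |
| −30 | about 3% | 3–6% |
| −40 | 0.4–0.6% | 0.5–2.5% |

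Under the null, each repair alone rejects in 0.10–0.11 of trials and the better of the two in 0.12–0.13. Choosing the covariance by AIC, as the SAP does, gives 0.12–0.14. A simpler known-covariance check at 30/4/15 and −20 gave 6–8% disagreement.

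**(b) Slope program**

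AR(1) on a 2×2 random-effects matrix is s²[[1, r], [r, 1]]: one variance for an intercept in percentage points and a slope in points per week. The SAP's AR(1)/CS/UN search covers only the REPEATED line of the means program.

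Worked case at 30/4/15, with no intercept–slope correlation:
- True slope-contrast SE: √[(2/30)(16 + 225/17.5)] = 1.39.
- The best tied fit has variance 43.4, r = 1 and residual 363.4, so its SE is √[(2/30)(43.4 + 363.4/17.5)] = 2.07. The ratio is 1.5.

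Simulated one-sided size at nominal 0.10, and power for −3 points per week:

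| SDs | Size, tied / UN | Power, tied / UN | SE overstated |
|---|---|---|---|
| 35/5/15 | 0.017 / 0.098 | 0.22 / 0.71 | 2.7× |
| 30/4/15 | 0.026 / 0.102 | 0.54 / 0.79 | 1.7× |
| 30/3/20 | 0.028 / 0.092 | 0.57 / 0.79 | 1.5× |
| 20/8/15 | 0.061 / 0.088 | 0.42 / 0.51 | 1.2× |
| 10/8/15 | 0.105 / 0.107 | 0.52 / 0.53 | 1.0× |

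A separate large-sample fit over the same five sets gave ratios of 1.0 to 3.2.

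**(c) Slope definition**

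The protocol's slope starts at baseline. The SAP's covers Weeks 1–6 with a free intercept per arm. For a constant −30 difference from Week 1 on, the coded slope difference is 0.

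**The case against.** *The fault will be caught.* Probably so. A contrast that cannot be computed is visible, and SAP 7 applies quality-control procedures to all output. A reader might infer that the primary analysis would go ahead on the two slope tests alone, with the heavy loss of power that this implies for an effect already present at Week 1. The documents do not support that: SAP 6.3.1 names four tests, and nothing permits dropping two.

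*The prose already settles the repair.* Largely. The SAP says that week is continuous in the model, which points to the fitted line. But the LSESTIMATE lines point to categorical week, Protocol 9.3.1.1 lists only treatment, time and their interaction, and neither document names the fitted line at Week 6 as the estimand. The choice is tilted, not fixed.

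*The numerical stakes are modest.* True. The inflation is 2 to 3 points of alpha, and at −40 points the repairs almost always agree.

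*The slope covariance is a preference.* In part. The tied form does not inflate alpha and does no harm at 10/8/15. The slope figures are one-sided, whereas the SAP's check of direction after a significant interaction suggests a two-sided p-value. Read them as relative loss.

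*The slope could be fitted from baseline.* A reader might infer this from the protocol, but it is not defined. Change from baseline is zero for everyone at Week 0. For the constant −30 effect, adding a Week 0 row gives −90/28 = −3.2 per week, and a line through the origin gives −30 × 21/91 = −6.9. Neither document chooses.

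**Conclusion.** (a) is wrong as written and must be corrected before any unblinded analysis. That rests on the MODEL and LSESTIMATE text and on how the procedure works, not on assumed variances; SAS itself was not run. The consequence is an unfixed choice between two different primary tests: verdicts differ in up to about 12% of trials at moderate effects and about 3–6% at −30, and null rejection is 0.12–0.13 rather than about 0.10 if the better one is picked. These sizes depend on the assumed SDs and time courses.

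(b) is a separate and cheap improvement. The slope SE is overstated by a factor of about 1 to 3, depending on how far the intercept SD exceeds the slope SD. The effect is lost power, not false positives.

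(c) is a minor difference in wording between protocol and SAP.

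**What to change.** **(a)** Since the SAP states that week is continuous, replace each LSESTIMATE line by an ESTIMATE of the `tx` difference plus 6 times the `tx*week_2` difference, and name the fitted line at Week 6 as the estimand. Use the matching week number for each secondary endpoint, and do the same for Stage 2. If categorical time is intended, write `MODEL cfb = tx week tx*week` and amend the prose. Either way, run the program on dummy data first and check the order of the treatment levels or, if LSESTIMATE is kept, how its bracketed level references are read. The cost is a few SAP lines and a dry run. The fitted line can misstate a curved course, as in step 5. Categorical week avoids that with slightly less power (0.71–0.72 against 0.74–0.77 at −20 points, 30/4/15).

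**(b)** Use `type=UN` on the RANDOM statement, with a stated fallback when the matrix is not positive definite, for example a refit constrained to be positive semidefinite. The cost is one more parameter and some boundary fits: at most 0.1% of trials in three of the five settings above, 10.5% at 30/3/20, 4.8% at 10/8/15, and 33% at 5/8/15. With the constrained refit at 30/3/20, size was 0.08 and power 0.79.

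**(c)** State in both documents that the slope covers Weeks 1–6. This is a wording change only.
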